2.0 Rationale and Hypotheses

As perfusion metrics in the healthy volunteers, patients with risk factors and/or coronary artery disease and in tissue with transmural myocardial infarctions has been well defined(13) AND same day test-retest variability minutes apart using a bolus infusion is $\pm 10\%$ (9), we shall test 3 hypotheses.

The first hypothesis is repeated same day test-retest coefficient of variation (COV) of whole heart rMBF and sMBF acquired using a bolus on a modern 3D PET scanner falls within $\pm 10\%$. The second hypothesis is repeated same day test-retest COV of whole heart rMBF and sMBF acquired using a low flow profile on a modern 3D PET scanner falls within $\pm 10\%$. The third hypothesis is COV of whole heart rMBF and sMBF between bolus and low flow profile is $\pm 10\%$ where the bolus is considered the standard on a modern 3D PET scanner.

The above testing and hypotheses deal with precision of MBF measurements however does not address accuracy. Measuring accuracy of non-invasive MBF measurements poses significant challenges as a “gold standard” for comparison is not realistically achievable in a clinical setting. Invasive measurements would pose unnecessary risk for patients and non-invasive “gold standard” measurements would require a standardized “phantom pump” which is not available within industry. Instead, PET labs have traditionally relied on patient populations to determine accuracy. As such, this study will not test nor is it powered to answer questions regarding accuracy. As the PET camera is currently being installed and testing prior to a “clinical go-live” is preferable to ensure measured flow metrics are consistent with the literature, as part of quality assurance, testing of the above hypotheses will also allow us to make additional observations to:

- 1) Confirm healthy volunteers measured rMBF and sMBF fall within published ranges (rMBF 0.69-1.06 cc/min/g and sMBF >2.17cc/min/g) .(13)
- 2) Confirm clinical volunteers with risk factors and/or CAD measured rMBF and sMBF fall within published ranges (rMBF 0.50-1.10 cc/min/g and sMBF >1.09 to 2.17 cc/min/g).(13)

- 3) Confirm rMBF in regions of infarct in volunteers with prior large myocardial infarctions fall within published ranges (rMBF <0.45 cc/min/g with minimum <0.19 cc/min/g).(14)

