3.0 Study Design and Population

This is a prospective, single center study from the Ochsner Medical Center. We seek to enroll a total of 85 paid volunteers that collectively encompass the range of physiology seen in routine practice. For simplicity sake, the range can be broken down into 3 distinct groups: 1) healthy volunteers without cardiac risk factors or chronic medical conditions (“normal”) 2) clinical patients with cardiac risk factors and/or history of clinical coronary artery disease (CAD), percutaneous coronary intervention (PCI) or coronary artery bypass grafting (CABG) (“clinical”) 3) patients with large myocardial infarctions demonstrated on prior PET stress testing (“infarct”). Volunteers will be recruited by “word-of-mouth” and through electronic records chart review. “Normal” volunteers will be consented and screened by history and laboratory tests for unrecognized cardiovascular risk factors, nicotine and caffeine. “Clinical” and “infarct” volunteers will not require laboratory tests other than caffeine levels. Once screened and consented, volunteers will undergo dipyridamole myocardial perfusion 3-D PET/CT stress testing with variable Rb-82 infusion profiles per the attached protocol. Female volunteers will also be questioned on their menstrual history and undergo urine pregnancy testing if appropriate on the day of the scan. The first 5 volunteers will be not be used in the final analysis but will be used to confirm proper scanner function, reconstruction settings and appropriate filter settings.

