7.0 Statistical Analysis

This is a measurement reliability study in a 2x2 factorial design. Study factors are infusion flow rate (20 or 50) at rest and stress. The linear nature of data acquisition takes about 45 minutes and yields five absolute values for each subject: three resting values and 2 stress values. The first 2 resting values and the 2 stress values condition are obtained in a cross-over fashion by infusion flow rate (infusion level assigned randomly for first resting scan and for first stress scan). The third resting value will be obtained at either a 20 or 50 infusion flow rate and will be used to determine precision (test-retest variability) against the same infusion profile obtained in the first two infusions.

Precision and variability will be determined for global, average quadrant, and individual pixel values of rest flow, stress flow and CFR. Standard summary statistical tests will be used. Applicable tests are 2-tailed, and $p < 0.05$ will be considered statistically significant. Linear regression will be reported between rest perfusion and rest pressure rate product (PRP). Paired or unpaired Student *t* test will be used to evaluate continuous variables where appropriate. The Pitman-Morgan *F* test will be used to test for differences in variability of perfusion between groups. To compare the histogram distribution between groups of stress perfusion and CFR for each of 1344 pixels as percentage of LV in color-

coded ranges of coronary flow capacity, we will use the Kolmogorov-Smirnov (KS) test for differences in histogram distribution.

8.0 Reporting of Adverse Events or Unanticipated Problems involving Risk to Participants or Others

Adverse events or unanticipated problems will be reported to [name] or [name] at [contact] and the Internal Review Board as directed by Ochsner Medical Center IRB rules and regulations.

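### The regression of rest flow on pressure-rate product names no allowance for three correlated rest scans per volunteer; pooling them as independent would understate the slope's standard error

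*Combined protocol and SAP*

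**What the plan says.** The regression gets one sentence in section 7.0: "Linear regression will be reported between rest perfusion and rest pressure rate product (PRP)". The same section says that data acquisition "yields five absolute values for each subject: three resting values and 2 stress values".

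The first two rest scans use the two infusion rates in random order ("infusion level assigned randomly for first resting scan and for first stress scan"). The third repeats one of those rates and "will be used to determine precision (test-retest variability) against the same infusion profile obtained in the first two infusions". Whether the third scan also enters the PRP regression is not stated.

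On inference, section 7.0 says: "Applicable tests are 2-tailed, and $p < 0.05$ will be considered statistically significant". No section names a volunteer effect, clustered standard errors or averaging over scans for this regression. None says whether PRP is recorded at each rest scan.

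On numbers, section 3.0 says "We seek to enroll a total of 85 paid volunteers" and "The first 5 volunteers will be not be used in the final analysis".

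**The concern.** Three rest scans from one person in one session share that person's flow level and, probably, much of that person's PRP. Simple linear regression assumes independent residuals. The reading that needs least added to the text is a scatter of all rest scans with one fitted line. That fit counts 240 observations where the information is worth fewer. The slope's standard error would then be too small, its confidence interval too narrow and its p-value too low.

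Two other simple applications avoid this at a price. Using one scan per volunteer leaves most of the rest data out. Using volunteer means gives only the slope between volunteers and says nothing about whether a person's flow follows that person's own PRP from scan to scan. The plan does not say which application or which slope is meant.

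**Working it through.** The plan gives no slope, standard error, interval or power figure for this regression, so there is no figure of its own to reproduce. Only the counts can be checked.

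**Counts (sections 3.0, 4.0 and 7.0).** Analysed volunteers: 85 − 5 = 80, which agrees with 40 + 20 + 20 = 80. Rest scans: 80 × 3 = 240.

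**Effect of pooling.** Let rx be the within-person correlation of PRP and ry that of the flow residual, with m = 3 scans per person.

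- Design effect: DEFF = 1 + (m − 1) × rx × ry = 1 + 2 × rx × ry
- True SE / pooled SE = √DEFF
- Actual type I error of a nominal 5% test = 2 × [1 − Φ(1.96/√DEFF)]

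The documents give neither correlation, so rx and ry are assumptions.

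| rx | ry | DEFF | SE ratio | Type I error | Effective scans (240/DEFF) |
|---|---|---|---|---|---|
| 0 | any | 1.00 | 1.00 | 5% | 240 |
| 0.5 | 0.5 | 1.50 | 1.22 | 11% | 160 |
| 0.8 | 0.5 | 1.80 | 1.34 | 14% | 133 |
| 0.8 | 0.8 | 2.28 | 1.51 | 19% | 105 |

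Simulating the last three rows (80 volunteers × 3 scans, no true association, 4,000 runs) gave SE ratios of 1.23, 1.34 and 1.49 and rejection rates of 11.2%, 14.0% and 18.6%. Over a wider assumed range (rx 0.5 to 1.0, ry 0.3 to 0.9), the ratio runs from 1.14 to 1.67 and the type I error from 8.6% to 24%.

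**Are such correlations plausible?** Section 2.0 gives rest-flow ranges of 0.69–1.06 (normal) and 0.50–1.10 cc/min/g (clinical), and test-retest variability of ±10%. Assume that each range is mean ± 2 between-person SD, and that ±10% is a within-person COV.

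- Normal: between-person SD (1.06 − 0.69)/4 = 0.0925; within-person SD 0.10 × 0.875 = 0.0875; correlation 0.0925²/(0.0925² + 0.0875²) = 0.53
- Clinical: between-person SD (1.10 − 0.50)/4 = 0.15; within-person SD 0.10 × 0.80 = 0.08; correlation 0.15²/(0.15² + 0.08²) = 0.78

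If the ranges already contain measurement error, the values become 1 − 0.0875²/0.0925² = 0.11 (normal) and 1 − 0.08²/0.15² = 0.72 (clinical). These are correlations of flow, not of flow after PRP is fitted, so they are only a rough guide to ry. Nothing in the documents bears on rx.

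**The alternatives.** A second simulation (20,000 runs, no association) compared four fits. The last two columns give the true SD of the estimated slope, in standardised units.

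| Fit | Type I error over four (rx, ry) cases | Slope SD at (0.9, 0.7) | Slope SD at (0.5, 0.5) |
|---|---|---|---|
| Pooled, independence assumed | 10.9% to 19.4% | 0.098 | 0.079 |
| Pooled, cluster-robust SE | 5.7% to 6.2% | 0.098 | 0.079 |
| Volunteer means | 4.8% to 5.2% | 0.105 | 0.114 |
| One scan per volunteer | 5.0% to 5.2% | 0.114 | 0.114 |

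The four cases are (0.9, 0.5), (0.9, 0.7), (0.8, 0.7) and (0.5, 0.5). At (0.9, 0.7) the pooled fit reports an average SE of 0.065 against a true SD of 0.098. One scan per volunteer leaves 240 − 80 = 160 scans (67%) unused. The precision comparison assumes that the within- and between-volunteer slopes are equal; in the simulation both are zero.

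**The case against.** The strongest reply is that the plan is silent here, and silence is not an error. A reader might infer that the 240 scans will be pooled as independent. The text does not say so, and it does not exclude a volunteer term or clustered standard errors. Nor is there any reported interval that could be called too narrow, because none is given. This stands: the inflation is conditional on pooling.

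A reader might also infer that the only choice is between narrow intervals and discarded data. That is not so. Regressing volunteer means is plain linear regression, uses every scan and holds its error rate. Its limit is that it estimates the between-volunteer slope only.

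A third tempting inference is that the within-person slope is the one the study needs, or that the COV results cannot be read without it. The documents do not support this. The three hypotheses and three further observations in section 2.0 do not use PRP, and no decision is tied to this slope. The within-person slope would help to show whether scan-to-scan change in rest flow follows physiology, but that is a benefit and not a stated aim.

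Finally, the correlations are assumed, and low values remove the problem. This also stands. Values near zero are, however, unlikely for scans of one person within a session of about 45 minutes.

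What the reply does not remove is that the plan names a method that assumes independence, for data with a planned threefold repeat, and gives no allowance for it.

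**Conclusion.** The point holds as a conditional weakness in a secondary analysis. Section 7.0 plans linear regression on a quantity measured three times per volunteer and names no allowance for the correlation. If the scans are pooled as independent, the slope's standard error is too small by a factor of about 1.2 to 1.5, and a nominal 5% test runs at about 11% to 19%. Those figures rest on assumed within-person correlations of 0.5 to 0.8 for both PRP and residual flow, and the inflation vanishes if either is near 0. One scan per volunteer and volunteer means are both valid, but the first uses a third of the scans and the second answers only the between-volunteer question. An all-scans analysis that respects the clustering is better than any of the three. None of the three COV hypotheses depends on this regression.

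**What to change.** Replace the sentence in section 7.0 with one that says:

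- all rest scans from analysed volunteers enter the regression of rest flow on PRP;
- the model is a linear mixed model with a random volunteer intercept and infusion rate as a covariate, because the first two rest scans differ in rate by design;
- the slope is reported with a 95% CI.

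Linear regression with cluster-robust standard errors by volunteer is an acceptable alternative; with 80 volunteers it ran slightly above 5% in the simulation.

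State also whether PRP is recorded at each rest scan. If it is, enter PRP as two terms, the volunteer's mean and the scan's deviation from that mean, and report both slopes. If PRP is recorded once per volunteer, the deviation term is zero throughout and only the between-volunteer slope can be estimated. The clustering must still be allowed for.

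The cost is a sentence or two of analysis text and no additional scans. Intervals will be wider than those from a pooled fit, and that width is the correct one.

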4.0 Inclusion/Exclusion Criteria

Normal Volunteers

The normal population will include 40 volunteers (20 men and 20 women).

Inclusion Criteria:

- Adults ≥ 18 and < 40 years old able to give informed consent.
- Ability to abstain from caffeine for 48 hours

Exclusion Criteria:

- Any chronic cardiac disease or condition (e.g., hypertension, hyperlipidemia)
- Any chronic systemic disease or condition (e.g., diabetes, systemic lupus, rheumatoid arthritis)
- Tobacco use
- Family history in a first degree relative with clinical CAD (h/o PCI, MI or CABG) in men < 55 or women < 65
- Severe claustrophobia
- Positive urine pregnancy test
- Inability to give informed consent
- BMI ≥ 30 or BMI > 25 and < 30 provided waist to hip ratio > 0.80 in women or 0.90 in men.

“Clinical” Volunteers

The “clinical” population will include 20 volunteers.

Inclusion Criteria:

- Adults ≥ 18 years old able to give informed consent.
- Any cardiac risk factor including hypertension, hyperlipidemia, diabetes mellitus or tobacco use OR
- CAD defined by with history of PCI or CABG, Coronary Ca score > 400 , or dense coronary calcifications noted on chest CT
- Ability to abstain from caffeine for 48 hours

Exclusion Criteria:

- Severe claustrophobia
- Hemodynamic instability or unstable symptoms
- Positive urine pregnancy test
- Inability to give informed consent

“Infarct” Volunteers

The “infarct” population will include 20 volunteers.

Inclusion Criteria:

- Adults ≥ 18 years old able to give informed consent.
- Prior cardiac PET scan demonstrating a fixed defect $\geq 15\%$ of the LV myocardium with relative uptake $\leq 60\%$ maximum uptake.
- In addition, to the perfusion defect, each volunteer requires either:
 - FDG PET or MRI viability studies confirming infarct OR
 - akinesis and wall thinning on ECHO within the same territory as the PET defect in addition to Q-waves on ECG
- Ability to abstain from caffeine for 48 hours

Exclusion Criteria:

- Severe claustrophobia
- Hemodynamic instability or unstable symptoms
- Positive urine pregnancy test
- Inability to give informed consent

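### Between-group comparisons should use Welch's t test: at 40 v 20 the pooled Student test is not protected against unequal variances and could run at about 9% for normal v clinical rest flow

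*Combined protocol and SAP*

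**What the plan says.** Section 7.0 has one sentence on t tests. It offers "Paired or unpaired Student" t "test will be used to evaluate continuous variables where appropriate". It names no endpoint, no contrast and no variance option, and Welch's test is not mentioned. The level is set for all tests together: "Applicable tests are 2-tailed, and $p < 0.05$ will be considered statistically significant".

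Section 4.0 fixes the group sizes. "The normal population will include 40 volunteers (20 men and 20 women"), and for both the clinical and the infarct group the "population will include 20 volunteers". Section 3.0 enrols 85 and adds that "The first 5 volunteers will be not be used in the final analysis", so 85 − 5 = 80 = 40 + 20 + 20 remain for analysis.

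Section 2.0 gives no SDs. It lists published ranges against which each group will be checked: for normals "rMBF 0.69-1.06 cc/min/g and sMBF >2.17cc/min/g", and clinical volunteers should "fall within published ranges (rMBF 0.50-1.10 cc/min/g and sMBF >1.09 to 2.17 cc/min/g"). For infarct regions it gives only upper limits on rest flow (below 0.45, with a minimum below 0.19 cc/min/g).

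**The concern.** The bolus and low-flow scans are made in the same volunteer, so comparing the two profiles calls for a paired test. The volunteer groups are then the most obvious place for the unpaired test, and normal v clinical and normal v infarct are both 40 v 20.

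The pooled test is robust to unequal variances when the groups are of equal size, but not at 2:1. If the smaller group is the more variable, the pooled standard error is too small and the test rejects too often. If the larger group is the more variable, the test is conservative.

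There is reason to expect the first pattern for rest flow. The published clinical range is wider. Eligibility points the same way: normals are under 40 and screened on blood pressure, lipids, nicotine and body size, whereas clinical volunteers may be any adult with a risk factor or coronary disease. At stake are the p-values for differences in flow between these groups.

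**Working it through.** **Inputs from the documents.** n₁ = 40 (normal) and n₂ = 20 (clinical), from section 4.0; two-sided α = 0.05, from section 7.0. Rest-range widths from section 2.0: normal 1.06 − 0.69 = 0.37; clinical 1.10 − 0.50 = 0.60.

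**Assumption, not in the documents.** Both ranges span the same number of SDs, so the SD ratio (clinical/normal) is 0.60/0.37 = 1.62 and the variance ratio is 2.63.

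**Formula.** In large samples the pooled variance of the difference tends to s₁²/n₂ + s₂²/n₁, while the true variance is s₁²/n₁ + s₂²/n₂. The actual size is therefore 2Φ(−1.96k), with

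k = √[(s₁²/n₂ + s₂²/n₁) / (s₁²/n₁ + s₂²/n₂)].

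**The plan's own figure.** With equal SDs, k = 1 and the size is 5.0%. The finite-sample calculation at 40 v 20 (58 df) also gives 5.0%. The stated level is right when the variances are equal.

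**SD ratio 1.62, clinical group more variable.**
- Pooled: 0.1369/20 + 0.36/40 = 0.006845 + 0.009 = 0.015845.
- True: 0.1369/40 + 0.36/20 = 0.0034225 + 0.018 = 0.0214225.
- k = √(0.015845/0.0214225) = √0.740 = 0.860, and 1.96 × 0.860 = 1.686, so the size is 9.2%.
- The finite-sample calculation, averaging over the distribution of the sample variances, gives 9.3%. Direct simulation gives 9.3% with normal data and 9.5% with uniform data.

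**Range over the assumed SD ratio (40 v 20, smaller group more variable).**

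| SD ratio | Pooled Student | Welch |
|---|---|---|
| 1.0 | 5.0% | 5.0% |
| 1.2 | 6.5% | 5.0% |
| 1.4 | 7.9% | 5.0% |
| 1.62 | 9.3% | 5.0% |
| 2.0 | 11.2% | 5.0% |

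**If the ranges are minimum to maximum.** The implied ratio then depends on the sizes of the source samples, which the documents do not give. As illustrations, 100 normals and 1000 clinical patients would imply a ratio of 1.25 and a size of 6.9%; 1000 and 100 would imply 2.10 and 11.6%.

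**Opposite direction.** If the group of 40 is 1.62 times as variable, the two variances above change places: (0.36/20 + 0.1369/40) / (0.36/40 + 0.1369/20) = 0.0214225/0.015845 = 1.352. Then k = 1.163 and the size is about 2.3%. Welch gives 4.9 to 5.0%.

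**Infarct contrasts.** The documents give no closed range here. Taking 0.45 − 0.19 = 0.26 purely as an illustrative width, normal v infarct (40 v 20) has size 2.9%, and clinical v infarct (20 v 20) has 5.3%.

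**Cost of Welch.** With equal SDs at 40 v 20 and a difference that gives the pooled test about 80% power, simulated power is 79.9% for the pooled test and 79.1% for Welch.

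**The case against.** The strongest reply is that the plan names no test of normal against clinical rest flow. The three hypotheses concern test-retest COV for each profile and COV between profiles, all within volunteer. The group ranges appear as extra quality-assurance observations, each group against its own range, and the t-test sentence leaves its use to judgement. Mention of groups elsewhere in section 7.0 may even mean infusion profiles, because the Pitman-Morgan test is for paired data. This stands. Between-group use is a natural inference but not a stated analysis, and the point touches secondary comparisons only.

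The second reply is that the ranges are not SDs. The documents do not say whether they are minimum to maximum, mean ± 2 SD or cut-offs, and the two stress ranges meet exactly at 2.17, which looks like a category boundary. This also stands. A reader might infer that the plan's own ranges contradict equal variances and that the error rate is 9% as a matter of fact. The documents do not support that: the ranges suggest unequal spread, and the 9% is conditional.

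The third reply is about scope. A reader might infer that every unpaired comparison is inflated, or that the unpaired test can only mean 40 v 20. Neither follows. Men v women among normals and clinical v infarct are both 20 v 20 and stay near 5%, and normal v infarct may be conservative. No width ratio can be formed for stress flow, because the normal range has no upper limit, or for CFR, for which no range is given.

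None of this weakens the case for Welch, which holds about 5% whichever assumption is true.

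**Conclusion.** The point holds in conditional form and is minor. The plan names a pooled-variance test, and two of the three possible volunteer-group contrasts are 40 v 20, where that test does not protect its level. For normal v clinical rest flow the actual type I error would be about 9% against a nominal 5%, provided that the comparison is made with the pooled test and that range width is proportional to SD. SD ratios from 1.2 to 2 give about 6.5% to 11%. If the larger group is the more variable, the error is in the conservative direction. The conclusions on the three COV hypotheses do not depend on this test.

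**What to change.** In section 7.0, replace the unpaired Student t test by Welch's unequal-variance t test for any comparison between volunteer groups, and report the confidence interval that goes with it. State in the same sentence which groups and which flow measures will be compared. The paired test for within-volunteer comparisons need not change. The cost is a few words in the SAP and less than one percentage point of power if the SDs turn out equal; sample size and data collection are unaffected.

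### The Kolmogorov-Smirnov comparison of pixel histograms fixes neither its unit of inference nor its groups; if pixels are pooled over subjects, its p-values are invalid

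*Combined protocol and SAP*

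**What the plan says.** Section 7.0 (Statistical Analysis) of the combined protocol and SAP sets applicable tests at two-tailed p<0.05. Its last analysis reads "To compare the histogram distribution between groups of stress perfusion and CFR for each of 1344 pixels as percentage of LV" and continues over the page with "coded ranges of coronary flow capacity, we will use the Kolmogorov-Smirnov (KS) test for differences in histogram distribution". No clustered, paired or permutation form of the test is named.

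**Unit.** The same section states that "Precision and variability will be determined for global, average quadrant, and individual pixel values of rest flow, stress flow and CFR", so pixels are a level of analysis in their own right. A percentage of the LV, however, could equally be one value per subject.

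**Groups.** Section 3.0 says of the volunteers that "the range can be broken down into 3 distinct groups". Section 7.0, by contrast, makes infusion flow rate the study factor: "The first 2 resting values and the 2 stress values condition are obtained in a cross-over fashion by infusion flow rate", with "infusion level assigned randomly for first resting scan and for first stress scan". The sentence just before the KS sentence says that the Pitman-Morgan F "test will be used to test for differences in variability of perfusion between groups", and Pitman-Morgan is a test for paired measurements. Both meanings are therefore open.

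**Related provisions.** Section 7.0 also plans paired or unpaired t tests for continuous variables, and it adds a further rest scan for test-retest precision: "The third resting value will be obtained at either a 20 or 50 infusion flow rate".

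**The concern.** The ordinary KS test assumes two independent samples of independent observations. Pixels from one heart are not independent: they rise and fall together with the subject's flow level and with any error common to the scan. Section 2.0 takes ±10% as the known same-day test-retest variability, so a common scan error is to be expected.

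The stake is largest for bolus against low flow. On the pixel reading, ordinary test-retest error could be reported as a significant difference between profiles. On the subject reading, the KS test would be almost uninformative. As written, the choice is left to the analyst and could be made after the data are seen. Between volunteer groups the pixel p-values are just as invalid but matter less, because section 2.0 already expects normal and clinical volunteers to differ in stress flow.

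**Working it through.** The plan contains no KS sample-size or error-rate figure to reproduce.

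**1. Sample sizes and critical distances.** Section 4.0 gives 40 normal, 20 clinical and 20 infarct volunteers. Adding the 5 run-in volunteers excluded in section 3.0 gives the 85 enrolled, so 80 are analysed. The 5% critical KS distance is 1.358 × √((n+m)/(n×m)).

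- Profiles, pooled pixels: 80 × 1344 = 107,520 per profile; critical distance 0.0059.
- Volunteers 40 v 20, pooled pixels: 53,760 v 26,880; critical distance 0.0101.
- Profiles, one value per subject: 80 v 80; critical distance 0.215.

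**2. Scan error.** Section 2.0 does not define ±10%. The per-scan error is 10/(1.96×√2) = 3.6% if it means 95% limits of the between-scan difference, 10/1.96 = 5.1% if 95% limits of one scan, 10/√2 = 7.1% if the SD of the difference, and 10% if the SD of one scan (the extreme).

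**3. Check by hand, profiles, pooled pixels.** Assume a stress-flow CV of 20% between subjects, 15% between regions and 10% pixel noise. With 5.1% scan error the total CV is √(20²+15²+10²+5.1²) = 27.4%. For a roughly normal distribution a small mean shift gives a KS distance of about 0.399 × shift/CV, so a shift of 0.0059 × 27.4/0.399 = 0.41% is enough to reject. Scan error alone gives the profile difference a standard error of 5.1 × √2/√80 = 0.81%. The threshold is thus about half a standard error, and it is passed by chance about 62% of the time through the mean alone.

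**4. Simulation, profiles, pooled pixels, no true difference.** 400 datasets per setting. Ranges cover independent or spatially correlated pixel noise, and a homogeneous or a 40/20/20 population. The bins are stand-ins: 1.09 and 2.17 (section 2.0) for stress flow, pooled tertiles for CFR.

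| Scan error | Stress flow, 3 bins | CFR, 3 bins | Unbinned |
|---|---|---|---|
| 3.6% | 41-51% | 68-81% | 87-98% |
| 5.1% | 62-63% | 82-89% | 96-100% |
| 7.1% | 74-78% | 89-96% | 99-100% |
| 10% | 83-89% | 94-97% | 99-100% |

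With no scan error the test rejects 0% under independent noise, and 19-50% (binned) or 71-81% (unbinned) under correlated noise.

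**5. Volunteer groups 40 v 20, pooled pixels, no true difference.** At a pixel intraclass correlation (ICC) of 0.01, the variance of a group mean is already 1 + 1343 × 0.01 = 14.4 times what independence implies. Simulated unbinned rejection at ICC 0/0.01/0.05/0.2/0.55 is 4/54/84/98/100% with independent noise and 94/93/94/99/100% with correlated noise. In three stress-flow bins it is 0/31/70/82/92% and 61/63/70/85/93%.

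**6. One value per subject, between profiles.** For a continuous value with between-scan correlation 0.5, 0.8, and 0.9 or more, the ordinary KS test rejects 0.8%, at most 0.08% and about 0% under the null. For simulated percentages of the LV it rejects 0-0.2% under the null, and 0-6% when a true 5% shift is present.

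**7. One value per subject, between volunteer groups.** For a continuous value the null rate is 4.4% (40 v 20) and 3.1% (20 v 20). It falls to 3.0% and 1.9% when half the subjects score 0% in a range, and to about 0.1% for both when 80% do.

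**8. Other readings.** The four above are not exhaustive. A separate test at each pixel would, for example, give 0.05 × 1344 = 67 expected false positives per comparison under the null.

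**The case against.** The strongest reply is that the study does not depend on this test. A reader might infer from step 6 that a real difference between profiles would be missed, or that the plan nowhere allows for the cross-over. The documents do not support either inference. Section 7.0 plans paired t tests where appropriate, and global values. If a paired t test is applied to whole-heart stress flow in 80 subjects, a 5% shift at the worst-case 10% scan error gives a ratio of 5/(10×√2/√80) = 3.16, or about 88% power; at 3.6, 5.1 and 7.1% scan error power is 100, 100 and 99%. This stands, and it confines the defect to the KS analysis.

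Second, volunteer groups are the natural meaning of the word, and they are selected to differ: infarct volunteers need a fixed defect of at least 15% of the LV (section 4.0). A null of no difference is then of little interest. This lowers the stakes for that comparison but does not make pooled-pixel p-values valid. It also leaves the paired Pitman-Morgan sentence unexplained.

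Third, the variances are assumed, and the simulated bins are not the coronary flow capacity ranges, whose cut-offs the documents do not give. This is correct, so the rates are illustrative. The direction of error on the pixel reading depends on a scan-level error or spatially correlated noise (profiles), or on some within-heart correlation (volunteers). The variability accepted in section 2.0 makes a scan-level error likely.

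**Conclusion.** The concern holds for the KS analysis. The section most readily suggests the pixel as the unit. On that reading the named test gives wrong p-values: 41-100% false rejection between profiles across the four interpretations of ±10%, and for 40 v 20 volunteers at ICC 0.01 or more, 54-100% unbinned and 31-93% in three stress-flow bins. On the subject reading it is far too conservative between profiles. Because one reading rejects too often and another almost never, defining terms alone is not enough; the method needs to change for the profile comparison.

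Two further inferences should be resisted. One is that a single value per subject between volunteer groups is simply well calibrated. It is valid, and near nominal (about 3-5%) for a continuous value, but very conservative in ranges where many subjects score 0%. The other is that the third rest scan will be averaged into one profile's CFR. Section 7.0 assigns that scan to precision and proposes no such averaging; the text merely leaves open which rest scan CFR uses.

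This is a secondary analysis with no stated decision resting on it. It should be fixed before analysis. Confidence is high on the ambiguity and on the invalidity of pooled-pixel p-values, lower on the exact rates.

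**What to change.** Change section 7.0 as follows.

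1. State which groups the KS comparison covers, and make the subject the unit of inference.
2. For bolus against low flow, keep the KS distance but take its p-value by swapping profile labels within subject, with rest and stress swapped together. The randomised first scans justify this. Alternatively, use a paired test on one pre-named percentage-of-LV summary. Simulated null rates are 2-7% and 3-7%.
3. For volunteer groups, use one percentage-of-LV value per subject, noting that KS is conservative where many score 0%, or permute whole subjects across groups (null rate 4-8% for 40 v 20, 3-7% for three groups; Monte Carlo error about ±2 points).
4. Otherwise report pixel-level KS distances descriptively, without p-values.
5. State that CFR for each profile uses its rest scan from the first two, cross-over, rest scans.
6. State that a non-significant result does not show agreement, which stays with the COV criterion.

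The cost is a few sentences and a short permutation script, with no extra scans. P-values will be larger. With 80 subjects, the methods in item 2 detect a true 5% shift in 98-100% of simulated datasets at 3.6-5.1% scan error, 89-98% at 7.1% and 60-77% at 10%. For a 3% shift the figures are 92-100% at 3.6%, 76-94% at 5.1%, 51-69% at 7.1% and 32-40% at 10%.
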